6.3.2. Follow-up Testing and Procedures

The following testing and procedures will be performed at all scheduled follow-up time points. This includes all of the following settings:

- 7 days (\pm 2) days after Cycle 1, Day 1 (D0);
- On Day 1 of any subsequent Cycle (N>1);
- 7 days (\pm 2) days after a decision to Escalate dose;
- 7 days (\pm 2) days after a decision to Hold vactosertib;
- 7 days (\pm 2) days after decision to Restart vactosertib following a Hold,
- 14 days (\pm 4) days after an initial decision to Maintain vactosertib dose, and
- Day 1 of the next cycle of vactosertib after at least two, consecutive 'Maintain' dose-adjustment decisions at the same dose level.

6.3.2.1. Pre-dose evaluation:

- 6.3.2.1.1. History and Physical Exam
- 6.3.2.1.2. Record palpated spleen size
- 6.3.2.1.3. Laboratory testing
 - CBC, CMP, Uric Acid, Phosphorus, LDH
- 6.3.2.1.4. EKG (QTc) in the event of a dose increase
- 6.3.2.1.5. Complete MPN-SAF-TSS (Myeloproliferative symptom assessment form total symptom score)(Appendix A)
- 6.3.2.1.6. Pill Counts to assess compliance (subjects return all vials at visit for pill counts).
- 6.3.2.1.7. Toxicity assessment (CTCAE v5 criteria)
- 6.3.2.1.8. Erythropoietic Response assessment ([see Table 3 and section 10.1](#))
 - 6.3.2.1.8.1. Record Interval PRBC Transfused Volume
 - 6.3.2.1.8.2. Record Current Hemoglobin
 - 6.3.2.1.8.3. Record Hemoglobin change = Current Hemoglobin – Baseline Hemoglobin (g/dL)
 - 6.3.2.1.8.4. If Day 1 of Cycle, serum EPO is measured.

6.3.2.2. Record Dose Adjustment Decision ([see Table 3 section 7](#)), the dose adjustment decision options are outlined in section 6.3.3

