2.2.1. Pharmacology and Toxicology

Vactosertib (INN name, other names: TEW-7197, EW-7197, EW7197) is a highly selective, potent inhibitor of the protein serine/threonine kinase activity of transforming growth factor (TGF)- β receptor type 1 (TGFBR1; also known as activin receptor-like kinase 5 [ALK5]). Vactosertib inhibits the phosphorylation of the ALK5 substrates SMAD2 and SMAD3, as well as the intracellular signaling of TGF β .

Nonclinical studies conducted to date include in vitro and in vivo pharmacology studies, and PK studies in mice, rats, and dogs. The safety of vactosertib was evaluated in an in vitro human hERG assay, in a CNS and respiratory safety study in rats, and in a cardiovascular safety study in conscious, telemetry-instrumented Beagle dogs. Vactosertib produced a concentration-dependent inhibition of hERG-mediated potassium currents from 10 to 100 μ M ($IC_{50} = 31.04 \mu$ M); no inhibition was observed at 1 μ M. No treatment-related changes in the safety pharmacology studies on the central nervous and respiratory systems tested in rats and dogs were observed after oral administration of vactosertib at doses of up to 100 mg/kg. With respect to cardiovascular effects of vactosertib in Beagle dogs, a NOAEL of at least 100 mg/kg was established for orally administered vactosertib.

The toxicological profile of vactosertib has been evaluated in a single-dose GLP study in rats, repeated-dose non-GLP studies up to 14 days in rats and dogs, repeated-dose GLP studies up to 28 days in rats and dogs, a 13-week repeated-dose GLP study in rats, and in GLP genotoxicity studies.

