4.2 Inclusion Criteria

- Age ≥ 18 years
- Patients meet the WHO 2016 criteria for a Ph-neg MPN (including PV, ET, MF, MDS/MPN, MPN-U).
- Patients with MF must have DIPSS+ Intermediate or High-risk MF (primary or post-PV/ET)
- Patients should be on a stable dose of current cytoreductive therapy for at least 3 months prior to C1D1.
- Anemia as defined by HGB < 10 g/dL, or transfusion of ≥ 2 packed red blood cell (PRBC) unit within the past 4 weeks with HGB ≤ 8.5g/dL. The anemia, in the investigator's opinion,

must be due to underlying MPN and not due to other causes such as the toxic effects of prior cytoreductive chemotherapy.

- Ineligible, unsuitable or refractoriness to ESA therapy defined as any of the following:
 - Serum erythropoietin (EPO) >125 U/L⁴.
 - Proven ESA unsuitability is defined by history of any of the following:
 - Loss of erythroid hematologic improvement while receiving stable or increased ESA dose; or
 - ESA-attributed toxicity that, in the treating physician's opinion, makes ESA therapy unsuitable for subject.
 - ESA refractoriness defined by lack of erythroid hematologic improvement to ESA:²⁷
 - Less than 1.5 g/dL increase in hemoglobin after at least 6 weeks of ESA therapy; or
 - Ongoing transfusion dependence that has not been reduced by >4 U over an 8-week period compared to ESA pre-treatment 8 weeks.
- ECOG Performance status ≤ 2
- Able to swallow tablets
- Able to give written informed consent
- Willing and able to comply with scheduled visits, treatment plans, tests and procedures.
- Acceptable Organ Function as defined by:
 - serum creatinine ≤ 2 mg/dL or > 50 mL/min/1.73m² by direct measure
 - AST(SGOT)/ALT(SGPT) ≤ 3 x institutional upper limit of normal
 - Total bilirubin ≤ 2 x institutional upper limit of normal

Note: Subjects with documented diagnosis of Gilbert's Syndrome resulting in elevated total bilirubin levels will be eligible provided all other eligibility criteria are met.

Note: Subjects with total bilirubin 2-3 mg/dL and direct (conjugated) bilirubin in the normal range will be eligible, provided all other eligibility criteria are met.

- Acceptable Cardiovascular status as defined by:
 - Mean QT interval corrected for heart rate using Fridericia's formula (QTcF) ≤ 450 ms for males, and ≤ 470 ms for females on screening ECG.

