6.1 Schedule of Assessments

Table 1a. Tier 1 schedule of trial events 6.1.1

Tier 1 Schedule of Assessments	Screening	Treatment Tier 1															
		Cycle 1				Cycle 2				Cycle 3				Cycle 4			
Pre-study D-28 to -1		Wk1 ^a	Wk2 ^a	Wk3 ^a	Wk4 ^a	Wk5 ^a	Wk6 ^a	Wk7 ^a	Wk8 ^a	Wk9 ^a	Wk10 ^a	Wk11 ^a	Wk12 ^a	Wk13 ^a	Wk14 ^a	Wk15 ^a	Wk16 ^a
Informed Consent Form	X																
Inclusion/Exclusion Criteria	X															X	
Enrollment	X																
Demographics	X																
Diagnosis	X																
Medical History ^b	X	X	X	X	X	X	X	X	X	X	X	X	X	X	X	X	
Vital Signs	X	X	X	X	X	X	X	X	X	X	X	X	X	X	X	X	
Physical Examination ^c	X	X	X	X	X	X	X	X	X	X	X	X	X	X	X	X	
Medications	X	X	X	X	X	X	X	X	X	X	X	X	X	X	X	X	
ECOG	X	X	X	X	X	X	X	X	X	X	X	X	X	X	X	X	
Toxicity / AE assessment		X	X	X	X	X	X	X	X	X	X	X	X	X	X	X	
Con Med assessment		X	X	X	X	X	X	X	X	X	X	X	X	X	X	X	
Blood tests ^d	X	X	X	X	X	X	X	X	X	X	X	X	X	X	X	X	
Troponin, BNP, CK-MB	X													X			
EPO level	X					X				X				X			
Pregnancy test	X																
Electrocardiogram (EKG) ^e	X	e	e	e	e	e	e	e	e	e	e	e	e	e	e	e	

End of Tier 1 – Patients meeting composite response and toxicity endpoint may continue to accrue

Echocardiography with Doppler ^f	X																								
Bone Marrow Aspirate and Biopsy	X																								X
Ultrasound (left upper quadrant)	X																								X
Research blood	X	X						X								X					X			X	
Research Bone Marrow	X																								X
Treatment Administration Form and Compliance assessment		X	X	X	X	X	X	X	X	X	X	X	X	X	X	X	X	X	X	X	X	X	X	X	
MPN-SAF form		X	X	X	X	X	X	X	X	X	X	X	X	X	X	X	X	X	X	X	X	X	X	X	
Record HgB level and HgB change ^g		X	X	X	X	X	X	X	X	X	X	X	X	X	X	X	X	X	X	X	X	X	X	X	
Record RBC transfusion history		X ^h	X	X	X	X	X	X	X	X	X	X	X	X	X	X	X	X	X	X	X	X	X	X	
Composite response and toxicity endpoint assessment																									X

a. Visits are weekly if there is a dose change (escalated or reduced or held for toxicity). Visits are biweekly if dose is maintained. Visits are extended to every 4 weeks (once per cycle) as long as dose is maintained for 4 weeks.

b. Must record baseline comorbidities, pre-existing symptoms

c. Spleen size should be recorded

d. Blood tests are: CBC, CMP, UA, Phosphorous, LDH

e. Electrocardiogram required at screening. Only required at subsequent visits in the event of a dose increase.

f. Echocardiogram or Cardiac MRI will be done once every 2 cycles (8 weeks or 56 days)

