6.3. Treatment Phase

6.3.1. Cycle 1, Day 1 (D0) Testing and Procedures:

- 6.3.1.1. 6.3.1.1. Pre-dose evaluation:History and Physical Exam
- 6.3.1.2. Record palpated Spleen size
- 6.3.1.3. Laboratory Testing
 - CBC
 - CMP
 - Uric Acid
 - Phosphorus
 - LDH
- 6.3.1.4. Establish and Record Baseline Hemoglobin: Baseline Hemoglobin is defined as the median hemoglobin within 28 days of Cycle 1, Day 1 (D0).
- 6.3.1.5. EKG (QTc) in the event of a dose increase
- 6.3.1.6. Complete MPN-SAF-TSS Myeloproliferative symptom assessment form total symptom score)³³ (Appendix A)
- 6.3.1.7. Record baseline co-morbidities and pre-existing symptoms.

- 6.3.1.2. Dispense study drug (vactosertib 50 mg tabs, #130) for cycle from research pharmacy and deliver to eligible subject during clinic visit.
- 6.3.1.3. Starting dose for Tier 1 is DL1. Subject will receive the one dose of vactosertib (DL1) under supervision of treating physician or research study nurse.
- 6.3.1.4. Research blood sample (20mL) will be collected either with SOC labs (if they are on a stable dose of vactosertib) or one hour after vactosertib dose (if dose of vactosertib is modified).
- 6.3.1.5. Subject will return for Follow-up Testing and Procedures (section 6.3.2) in 7 (\pm 2) days after first dose of vactosertib.

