6.3.2.3. Dose Adjustment Testing and Procedures (*section 6.3.2.2*)

6.3.2.4. If Day 1 of Cycle,

- Pill Counts to assess compliance (subjects return all vials at visit for pill counts).
- Dispense study drug (vactosertib 50 mg tabs) for one cycle from research pharmacy and deliver to subject during clinic visit.
- Research blood sample (20mL) will be collected one hour after vactosertib dose (also collected on C1D8).

6.3.3. **Dose Adjustment Decision** ([see Table 3 section 7](#))

6.3.3.1. **Escalate** to next dose level

- Subject will receive one dose of vactosertib at escalated dose level under supervision of treating physician or research study nurse.
- Research blood sample (20mL) will be collected approximately 1hr after escalated dose taken.
- If dose is at maximum level (DL4), and patient has at least stable disease, then patient can remain on study at maximum level (DL4).
- If dose is at maximum level (DL4), and patient has progressive disease, then patient will be removed from study.
- Subject will return for Follow-up Testing and Procedures in 7 (\pm 2) days from start of new dose level.

6.3.3.2. **Maintain** current dose level

6.3.3.2.1. **New Maintain Decision:**

- Subject will return for Follow-up Testing and Procedures in 14 (\pm 3) days.

6.3.3.2.2. **Ongoing Maintain Decision:**

- After at least two, consecutive Maintain dose-adjustment decision at the same dose level, subject will return for Follow-up Testing and Procedures no later than Day 1 of the next cycle of vactosertib.

6.3.3.3. **Hold** vactosertib

- If last dose received is at minimum dose level (DL0), patient will be removed from study. Otherwise:

6.3.3.3.1. **New Hold Decision**

- Subject will return for Follow-up Testing and Procedures in 7 (\pm 2) days.

6.3.3.3.2. **Ongoing Hold Decision**

- If dose is held > 28 days, subject will be removed from study.
- If dose is held < 28 days, subject will return for Follow-up Testing and Procedures in 7 (\pm 2) days

6.3.3.4. **Restart** vactosertib

- Vactosertib dose will be reduced to one dose level lower than the last dose level received.
- If last dose received was at minimum dose level (DL0), patient should have already been removed from study.
- Subject will return for Follow-up Testing and Procedures in 7 (\pm 2) days from start of new dose level.
- Subject will receive one dose of vactosertib at restarted dose level under supervision of treating physician or research study nurse.

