6.3.5.3. Abdominal Sonogram of upper left quadrant to record Spleen size

6.3.5.4. EKG (QTc) in the event of a dose increase

6.3.5.5. Complete MPN-SAF-TSS (Myeloproliferative symptom assessment form total symptom score)(Appendix A)

6.3.5.6. Bone marrow aspirate and biopsy to assess response.

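### No on-study EKG is scheduled after a dose: the recurring one is a pre-dose test tied to a dose increase, so it is poorly placed to show a QTc effect

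*Combined protocol and SAP*

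**What the plan says.** Four instructions govern EKGs after screening, and all carry the same condition.

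- **Section 6.1, footnote e (both tier tables):** "Electrocardiogram required at screening. Only required at subsequent visits in the event of a dose increase". No timing relative to the dose is given.
- **Section 6.3.1.5 (Cycle 1 Day 1):** the same condition, in the list opened by the pre-dose heading.
- **Section 6.3.2.1.4 (every follow-up visit):** "EKG (QTc) in the event of a dose increase", under the pre-dose evaluation heading of 6.3.2.1.
- **Section 6.3.5.4 (End of Tier):** the same condition, with no timing relative to the dose.

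Section 6.3.3.1 (Escalate) requires a supervised dose at the new level and then a blood sample: "Research blood sample (20mL) will be collected approximately 1hr after escalated dose taken". It lists no EKG. The periodic cardiac evaluation in 6.3.4.1 lists an echocardiogram, troponin, BNP and CK-MB, also without an EKG. Section 13 names electrocardiographs as a general safety investigation but gives no schedule.

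On the drug itself, section 2.2.1 states: "Vactosertib produced a concentration-dependent inhibition of hERG-mediated potassium currents". The range was 10 to 100 µM with an IC50 of 31.04 µM, and there was no inhibition at 1 µM. The same section gives a cardiovascular NOAEL of at least 100 mg/kg in dogs.

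**The concern.** The protocol treats QTc as relevant: it reports a hERG signal and screens on QTcF. A first primary objective is a safe and tolerable dose, and the Table 3 rules can take a patient from DL1 (50 mg BID) to DL4 (200 mg BID). If QTc is read mainly when little drug is in the blood, an unremarkable record may reflect the timing of the test as much as the drug.

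The record feeds decisions. Dose-limiting toxicity includes non-hematologic toxicity of grade 3 or higher. DLTs drive the stopping rules (8.1), the Tier 2 starting level (6.3.6.3) and the composite response and toxicity endpoint (12.2.2, Table 5). A QTc change without symptoms can enter that count only if an EKG captures it. Patients who continue under 6.3.7 may be treated for up to 2 years.

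**Working it through.** The plan gives no figure on this point, so there is none to reproduce. Two checks were made.

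**1. How much drug is present at a pre-dose EKG**

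Inputs:
- Twice-daily dosing, 5 days on and 2 off (7.7).
- Visit 7 ± 2 days after a new dose level starts (6.3.3.1).
- Mean half-lives from 1.69 to 6.92 h (section 2.2.1, Tables 1 and 2), with 3.68 h for 200 mg BID on Day 5.
- Half-lives after repeated dosing spanning 0.4 to 18.1 h (2.2.1 text).
- Median time to peak of about 0.4 to 1.8 h (Tables 1 and 2).

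Assumptions: doses 12 h apart, a morning visit before the dose, and single-exponential decline. The protocol describes multi-exponential decline, so this is an approximation.

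Formula: fraction left = 0.5^(gap / half-life).

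If a level starts on Day 1, a visit 7 days later is Day 8, the first dosing day after the break. From the evening of Day 5 to the morning of Day 8 is 12 + 24 + 24 = 60 h. Days 9 and 10 are dosing days with a 12 h gap. Days 6 and 7 are off days, with gaps of 12 and 36 h.

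| Half-life | 60 h gap | 12 h gap |
|---|---|---|
| 1.69 h (shortest mean) | about 0% | 0.5^(12/1.69) = 0.7% |
| 3.68 h (200 mg BID, Day 5) | 0.5^(60/3.68) = 0.001% | 0.5^(12/3.68) = 10% |
| 6.92 h (longest mean) | 0.5^(60/6.92) = 0.25% | 0.5^(12/6.92) = 30% |
| 18.1 h (extreme) | 0.5^(60/18.1) = 10% | 0.5^(12/18.1) = 63% |

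Counting from a peak at 1 h instead of from the dose changes little: at 6.92 h the figures become 0.27% and 33%.

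The blood draw about 1 hour after the escalated dose, by contrast, falls close to the peak. Because section 2.2.1 reports negligible accumulation (median AUC ratio 0.75 to 1.16), exposure after the first dose at a level should be close to exposure later at that level.

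**2. Which dose levels get an EKG**

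Take the fastest path from DL1, with increases on Days 8, 15 and 22.

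| Reading of the condition | EKG days | Level the patient has been taking | Level never measured |
|---|---|---|---|
| A: visit where the increase is decided, before the new dose | 8, 15, 22 | DL1, DL2, DL3 | DL4 |
| B: first visit after the increase | 15, 22, 29 | DL2, DL3, DL4 | DL1 |

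On either reading, a patient kept at the starting level has no required on-drug EKG.

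**Concentration context**

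Mean Cmax at 200 mg BID ranges from 2040 to 3746 ng/mL (Tables 1 and 2). Molecular weight is not in the documents. Assuming 300 to 500 g/mol, this is 2040/500 = 4.1 to 3746/300 = 12.5 µM of total drug, or 13% to 40% of the IC50 (4.1/31.04 to 12.5/31.04). Free drug would be lower. This shows only that the tested hERG range is not remote; it does not predict an effect.

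**The case against.** The strongest reply is that the prior risk looks modest and that the text is ambiguous more than wrong. There was no hERG inhibition at 1 µM, the IC50 is 31.04 µM, and the dog study gave a cardiovascular NOAEL of at least 100 mg/kg. The DL4 dose has been given before, and 300 mg BID produced no DLT in 3 patients (2.2.3). No QT term appears in Tables 6 to 11 of section 13, although the documents do not say when EKGs were taken in those trials. QTcF limits, cardiac exclusions, echocardiograms and cardiac markers are also in place. All of this stands and lowers the expected risk, but none of it puts an EKG near peak concentration.

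Three stronger readings are tempting, and the documents do not support them.

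- **That every on-study EKG is pre-dose.** Footnote e and 6.3.5.4 give no timing, and section 13 leaves room for unscheduled EKGs. What the text supports is that none is scheduled after a dose.
- **That these EKGs cannot detect a QTc effect.** A 12 h trough can hold up to about 30% at the mean half-lives and more at the extreme, so sensitivity is limited but not absent.
- **That patients at DL4 go unmeasured, or that DL4 is the level held longest.** The first depends on reading A. The second depends on hemoglobin response and toxicity, which the plan cannot fix in advance.

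**Conclusion.** The point holds as a weakness in safety measurement. After screening, every EKG instruction depends on a dose increase, the recurring one is pre-dose, and none is placed after a dose. At a visit exactly 7 days after a level starts, 0.25% or less of drug remains at the mean half-lives (about 10% at 18.1 h). At a 12 h trough roughly 1 to 30% remains at the mean half-lives. The coverage gap is DL4 on reading A and DL1 on reading B, and on both readings it includes any patient who stays at the starting level.

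The residual figures rest on 12-hourly dosing, a morning visit before the dose and single-exponential decline. The day counts rest on a DL1 start with weekly increases; a different Tier 2 starting level would change them. Nothing here shows that vactosertib prolongs QTc, and the sample size and efficacy analysis are unaffected.

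**What to change.** - Reconcile footnote e (both tables), 6.3.1.5, 6.3.2.1.4 and 6.3.5.4 so that each names the visit and the timing relative to the dose.
- Take the dose-increase EKG about 1 hour after the supervised escalated dose, alongside the blood draw already required in 6.3.3.1. This also puts a reading on DL4 for every patient who is escalated to it.
- Record time since last dose with every EKG.
- At Cycle 1 Day 1 and End of Tier, the dose-increase condition does not fit the visit. State whether an EKG is intended there. The answer at Cycle 1 Day 1 also settles whether patients who stay at the starting level are meant to have no on-drug EKG. A post-dose EKG at End of Tier is not proposed, because 6.3.5 schedules no supervised dose.

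**Cost:** protocol wording and one data field. The number of EKGs and visits is unchanged, and the 1-hour wait already exists at each escalation. **Downside:** an EKG taken only after the escalated dose no longer serves as a check before escalation. Keeping the pre-dose EKG as well avoids that, at one extra EKG per increase (three on an uninterrupted path from DL1 to DL4).

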6.3.2.3. Dose Adjustment Testing and Procedures (*section 6.3.2.2*)

6.3.2.4. If Day 1 of Cycle,

- Pill Counts to assess compliance (subjects return all vials at visit for pill counts).
- Dispense study drug (vactosertib 50 mg tabs) for one cycle from research pharmacy and deliver to subject during clinic visit.
- Research blood sample (20mL) will be collected one hour after vactosertib dose (also collected on C1D8).

6.3.3. **Dose Adjustment Decision** ([see Table 3 section 7](#))

6.3.3.1. **Escalate** to next dose level

- Subject will receive one dose of vactosertib at escalated dose level under supervision of treating physician or research study nurse.
- Research blood sample (20mL) will be collected approximately 1hr after escalated dose taken.
- If dose is at maximum level (DL4), and patient has at least stable disease, then patient can remain on study at maximum level (DL4).
- If dose is at maximum level (DL4), and patient has progressive disease, then patient will be removed from study.
- Subject will return for Follow-up Testing and Procedures in 7 (\pm 2) days from start of new dose level.

6.3.3.2. **Maintain** current dose level

6.3.3.2.1. **New Maintain Decision:**

- Subject will return for Follow-up Testing and Procedures in 14 (\pm 3) days.

6.3.3.2.2. **Ongoing Maintain Decision:**

- After at least two, consecutive Maintain dose-adjustment decision at the same dose level, subject will return for Follow-up Testing and Procedures no later than Day 1 of the next cycle of vactosertib.

6.3.3.3. **Hold** vactosertib

- If last dose received is at minimum dose level (DL0), patient will be removed from study. Otherwise:

6.3.3.3.1. **New Hold Decision**

- Subject will return for Follow-up Testing and Procedures in 7 (\pm 2) days.

6.3.3.3.2. **Ongoing Hold Decision**

- If dose is held > 28 days, subject will be removed from study.
- If dose is held < 28 days, subject will return for Follow-up Testing and Procedures in 7 (\pm 2) days

6.3.3.4. **Restart** vactosertib

- Vactosertib dose will be reduced to one dose level lower than the last dose level received.
- If last dose received was at minimum dose level (DL0), patient should have already been removed from study.
- Subject will return for Follow-up Testing and Procedures in 7 (\pm 2) days from start of new dose level.
- Subject will receive one dose of vactosertib at restarted dose level under supervision of treating physician or research study nurse.
- Research blood sample (20mL) cycle 1 will be collected approximately 1hr after dose taken.

6.3.4. **Additional Scheduled Studies and Procedures:**

Additional studies will be performed at regular intervals for all Subjects independent of the current dose of vactosertib; provided the indicated studies have not already been performed within 7 days.

6.3.4.1. Cardiac Evaluation after every three cycles is completed (every 84 \pm 7 days):

- Transthoracic Echocardiogram
- Cardiac troponin, BNP, CK-MB

6.3.4.2. Serum EPO is measured on Day 1 of each cycle (every 28 \pm 3 days).

6.3.4.3. Subjects will maintain a diary to record adverse events that occur between clinic visits (e.g., patient diaries).

6.3.5. **End of Tier Testing and Procedures:**

At the end of Cycle 4 (approximately Week 16 \pm 7 days), the following procedures will be performed for all Subjects.

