7.7.2 Dosing Delays/Dose Modifications for vactosertib

Clinical Parameter	Escalate to Next Dose Level	Maintain Current Dose Level	Hold Dose	Restart After Dose Hold
Erythropoietic Response	Inadequate	Adequate		
Hemoglobin (HGB) absolute value, change in HGB from baseline*, and Erythrocyte transfusion	HGB ≤10 g/dL AND ≤2 g/dL increase from baseline HGB OR any Erythrocyte transfusion	HGB >10 g/dL OR >2g/dL increase from baseline HGB AND No Erythrocyte transfusion	HGB >12 g/dL	HGB<12 g/dL
Current Toxicity (CTCAE v5)	≤Grade 2	≤Grade 2 OR >Grade 2 not requiring change in treatment	>Grade 2 Requiring Change in Treatment	<Grade 2 and Requiring No New Change in Treatment
Dose hold Toxicity during Cycle	Dose Hold Not Required During Cycle	Dose Hold Not Required During Cycle		
Current Dose Dose Levels: (DL0) 50 mg daily; (DL1) 50 mg bid; (DL2) 100 mg bid; (DL3) 150 mg bid; (DL4) 200 mg bid.	< Highest Dose Level	≤ Highest Dose Level		Most Recent Dose >(DL0)
Dosing schedule, 5 days on, 2 days off				
Rule	All True	All True	Any True	All True
Next Study Visit [†]	7±2 days	1 st Maintain [§] 14±3 days 2 nd or greater Maintain D1 of next cycle	7±2 days	7±2 days

Table 3: Intrapatient Dose Adjustment Rules.

The parameters shown are used to adjust the vactosertib dose on a continuing basis. The dose is escalated to the next level if ALL criteria for escalation are met. The decision to Hold vactosertib is made if ANY hold criteria is met at any point during the cycle. Otherwise the dose level is maintained. The criteria to Escalate, Maintain or Hold a dose are non-overlapping. Dose decrements by one level will follow any HOLD. * Baseline HGB is defined as the median HGB in the 4 weeks prior to D1 of protocol treatment. † Subject will maintain a diary of adverse events between study visits. [§]Visits are weekly if there is a dose change (Escalate, Hold or Restart). Visits are bi-weekly if the decision is to Maintain the current dose. Visits are extended to every 4 weeks (D1 of each new cycle) after the second or greater, consecutive Maintain decision.

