7.9 Duration of Therapy and Criteria for Removal from Study

- 7.9.1. Tier 1 duration is 16 weeks (4 treatment cycles) and Tier 2 duration is 24 weeks (6 treatment cycles).
- 7.9.2. In the absence of treatment delays due to adverse event(s), treatment may continue for 6-10 cycles or until one of the following criteria applies:
 - 7.9.2.1. Disease progression at the MTD,
 - 7.9.2.2. Intercurrent illness that prevents further administration of treatment,
 - 7.9.2.3. Unacceptable adverse events, specifically:
 - Adverse event(s) that necessitate a dose hold for >28 days,
 - Adverse events that occur at DLO
 - 7.9.2.4. Patient decides to withdraw from the study, or
 - 7.9.2.5. General or specific changes in the patient's condition render the patient unacceptable for further treatment in the judgment of the investigator.

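### Section 6.3.3.3 removes a subject on a long hold or a DL0 hold even when the only cause is haemoglobin above 12 g/dL, and the 4-cycle wording in 12.6.2 can leave a haemoglobin responder unassessed

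*Combined protocol and SAP*

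**What the plan says.** **Holds.** Table 3 (section 7.7.2) has two hold criteria: haemoglobin above 12 g/dL, and toxicity above Grade 2 that requires a change in treatment. Either is enough: "The decision to Hold vactosertib is made if ANY hold criteria is met at any point during the cycle". Restart needs haemoglobin below 12 g/dL, toxicity settled, and a most recent dose above DL0.

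**Removal, version one.** Section 6.3.3.3 states "If last dose received is at minimum dose level (DL0), patient will be removed from study" and, for a continuing hold, "If dose is held > 28 days, subject will be removed from study". No cause is given in either line. Section 6.3.3.4 repeats the DL0 removal ("If last dose received was at minimum dose level (DL0), patient should have already been removed from study") and lowers the dose after each hold: "Vactosertib dose will be reduced to one dose level lower than the last dose level received".

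**Removal, version two.** Section 7.9.2.3 lists the same two grounds, but under unacceptable adverse events: "Adverse event(s) that necessitate a dose hold for >28 days" and "Adverse events that occur at DLO". Section 8 refers the reader to 7.9, and the Data and Safety Monitoring Plan (section 15) names 7.9 as the place for individual stopping rules.

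**Who is counted.** Table 5 (section 12.2.2) defines a responder as a subject with clinical benefit for at least 8 weeks and no DLT. Table 4 needs at least 1 responder of 12 to proceed and at least 4 of 37 for success, and the early-stopping sentence in 12.1.1 counts subjects treated. None of these sets a minimum number of cycles. Section 12.6.2 assesses response only in patients who have received 4 cycles or more, and says the section is still to be completed.

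**The concern.** Entry requires haemoglobin below 10 g/dL, or recent transfusion with haemoglobin at or below 8.5 g/dL (section 4.2). Without transfusion, passing 12 g/dL is therefore a rise of more than 2 g/dL, above the 1.5 g/dL that defines an erythropoietic response in 10.1.3. In a trial of anaemia, the subjects who meet the haemoglobin hold are among the clearest responders.

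Two things are at stake. The first is treatment: a subject removed this way does not complete planned therapy, and completion is the entry point to the option in 6.3.7 to continue vactosertib. The second is the count: if such a subject has received fewer than 4 cycles, 12.6.2 read literally leaves a possible responder outside the assessment. One responder can decide whether Tier 2 opens.

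**Working it through.** **1. The plan's own figure.** Inputs from Table 4: 12 then 25 subjects, proceed at 1 or more, success at 4 or more of 37, response rates 0.05 and 0.20.

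P(success) = Σ over x ≥ 1 of Bin(x; 12, p) × P(Bin(25, p) ≥ 4 − x)

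- p = 0.05: 0.093 (plan: below 0.10)
- p = 0.20: 0.902 (plan: above 0.90)

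The design reproduces. Its power margin is 0.902 − 0.900 = 0.002.

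**2. Timing of removal.** A cycle is 4 weeks, so planned treatment ends at day 112 in Tier 1 (16 weeks) and day 168 in Tier 2 (24 weeks). Removal follows a hold of more than 28 days. Removal before the Tier 1 end therefore needs a hold that starts before day 112 − 28 = day 84.

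Both examples count only days on drug toward the 8 weeks, so they do not depend on whether hold weeks count.

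| | Example A | Example B |
|---|---|---|
| Benefit first recorded | day 21 | day 28 |
| Haemoglobin above 12, hold starts | day 77 | day 84 |
| Benefit on drug | 77 − 21 = 56 days | 84 − 28 = 56 days |
| Cycles received | 77/28 = 2.75 | 84/28 = 3 |
| Removed if still held after | day 105 | day 112 |

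With no DLT, both subjects meet Table 5.

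- Example A, Tier 1: the removal rule acts before Week 16.
- Example B, Tier 1: day 112 is already the planned end. The subject is short of 4 cycles because of the hold, and only the 12.6.2 wording leaves the subject unassessed.
- Example B, Tier 2: removal gives up 168 − 112 = 56 scheduled days, twice the 28 days a fourth cycle needs.

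**3. The DL0 route.** Tier 1 starts at DL1, and each hold lowers the dose one level. A hold at DL0 is the second hold for a subject who never left DL1, and the third, fourth or fifth for one who reached DL2, DL3 or DL4. Table 3 escalates a subject with inadequate response from the first visit at about day 7 (one trigger reads "increase from baseline HGB OR any Erythrocyte transfusion"), so this route is rare. It could be a first hold only if Tier 2 started at DL0, which 6.3.6.3 does not rule out.

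**4. Effect on the decision rule (illustration).** The documents give no rate for these losses. Assume a share L of responders is counted as failures, with 12 and 37 kept as denominators, so p = 0.20(1 − L).

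| L | p | Power |
|---|---|---|
| 0 | 0.200 | 0.902 |
| 2% | 0.196 | 0.895 |
| 5% | 0.190 | 0.882 |

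Solving for power 0.90 gives L = 0.0063. With 37 × 0.20 = 7.4 expected responders, that is 0.0063 × 7.4 = 0.05 of a responder.

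**5. How often one subject decides (p = 0.20).**

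- Exactly one Tier 1 responder: 12 × 0.20 × 0.80^11 = 0.206.
- Tier 1 passed and exactly 4 of 37: 0.902 − 0.848 = 0.054, where 0.848 is the chance of passing Tier 1 with 5 or more of 37.

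**The case against.** **The protocol points to 7.9 for removal.** Section 8 and the monitoring plan both do, and 7.9.2.3 ties these removals to adverse events. This is a documented basis for reading 6.3.3.3 narrowly. It stands as a reason to resolve the conflict in favour of 7.9. It does not remove the conflict: staff working through the hold procedure meet an unqualified instruction to remove.

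**A reader might infer that the removal rule is what costs Tier 1 its responders.** The documents do not support this in general. For a hold from day 84 onward, removal comes no earlier than the planned end, and end-of-Cycle-4 testing, including the erythropoietic assessment, is due for all subjects (section 6.3.5). There the 4-cycle wording alone is at issue.

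**A reader might also infer that these subjects will be dropped from the counts.** That is not established. Section 12.6.2 is marked as unfinished, Tables 4 and 5 set no cycle minimum, and haemoglobin, transfusions and symptoms are recorded at hold visits. An analyst using only Tables 4 and 5 could count the subject. What remains is that the plan allows two answers.

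**The power figures do not measure the problem.** This stands. The 2% and 5% losses are assumed. The 0.6% figure mainly shows how close to 0.90 the integer design lands. The 0.206 and 0.054 are chances that one subject is decisive, not chances of harm; each would have to be multiplied by an unknown and probably small probability of such a loss.

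**The route is narrow.** Also true. Removal through the 28-day rule needs haemoglobin to stay above 12 g/dL off drug for more than four weeks. Once it falls below 12, restart is allowed if toxicity permits and the last dose was above DL0.

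**Conclusion.** The text is wrong as written, with low expected frequency. There are two separate faults.

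1. Section 6.3.3.3 conflicts with 7.9.2.3 on whether a hold for haemoglobin alone can end a subject's participation. Section 7.9.2 is permissive, so this is an unqualified rule in one section against a narrower list in another, rather than two opposite instructions. In Tier 2 the literal rule cuts planned treatment short and closes off the 6.3.7 option; in Tier 1 it acts before Week 16 only for holds starting before day 84.
2. The 4-cycle condition in 12.6.2, read literally, excludes subjects who already satisfy Table 5. It reaches any early leaver, and haemoglobin holds are a small part of that group.

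The direction is certain: any resulting error counts against an active drug. The size is not. No substantial loss of power is shown, and nothing here says the Table 4 design is miscalculated. The conclusion assumes that 6.3.3.3 and 12.6.2 are applied as worded and that cycles received means cycles of dosing. It is worth correcting because one responder can decide Tier 2 and the correction is cheap.

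**What to change.** 1. **Sections 6.3.3.3 and 6.3.3.4.** Limit the 28-day and DL0 removals to toxicity holds as Table 3 defines them (above Grade 2 and requiring a change in treatment), and change the DL0 line in 6.3.3.4 to match. A subject held for haemoglobin above 12 g/dL alone then stays on study. The DL0 wording of 7.9.2.3 should not be borrowed, because it states no grade.
2. **Section 12.6.2.** Replace the 4-cycle condition with a rule that all treated subjects stay in the 12 and the 37 and are classified by Table 5 regardless of cycles received; those not shown to meet it count as non-responders.

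Whether a subject may restart at DL0 after a haemoglobin-only hold is a dosing choice for the sponsor and is not part of this change. The same applies to whether hold weeks count toward the 8 weeks, which should be fixed in advance.

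Cost: wording edits in three places and possibly some further hold visits for subjects whose haemoglobin stays above 12 g/dL beyond 28 days. The measurements are already scheduled, toxicity-hold removals under 6.3.3.3 are unchanged, and 12.6.2 has to be completed anyway.
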